	
WBRT >28 days ago will be eligible if asymptomatic and off systemic steroids.
 

6. Life expectancy of greater than 12 weeks.

7. Normal organ and marrow function as defined per protocol definitions.

8. Excludes patients who follow a vegan or vegetarian diet

STATISTICAL CONSIDERATIONS	
The primary objective is to evaluate efficacy of ONC201 with a methionine-restricted diet in metastatic TNBC. The study is designed as a single-arm phase II trial. The primary endpoint is ORR. Secondary endpoints include CBR, PFS, OS, safety, metabolic indices and CTC TRAIL-receptor expression. The null hypothesis is that the probability of ORR is no more than 0.1, i.e., <math>H_0: p \leq 0.1</math>, and the alternative hypothesis is <math>H_1: p \geq 0.25</math>. In this single arm study, a Simon's two stage design will be utilized. The null hypothesis that the true ORR is 0.1 will be tested against a one-sided alternative. The study will be powered to detect an ORR of 25% with the combination of ONC201 with a methionine-restricted diet, using a power of 80% and a type I error rate of 10%. The first stage sample size will be 13. After testing the combination on 13 subjects in the first stage, the trial will be terminated if 1 or fewer subjects respond. If the trial goes on to the second stage, a total of 34 subjects will be studied (i.e. additional 21 subjects will be recruited). If the total number responding or having ORR is less than or equal to 5, the combination of ONC201 with a methionine-restricted diet will be rejected.
 
Time to event outcomes such as PFS and OS will be analyzed using Kaplan-Meier method and Cox proportional hazards regression.

TOTAL NUMBER OF SUBJECTS	Number of subjects in the phase II study: 34
ESTIMATED ENROLLMENT PERIOD	Estimated 30 months
ESTIMATED STUDY DURATION	Estimated 36 months

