## 7. STUDY CALENDARS AND EVALUATIONS

Cycle = 21 days	Screening	Cycle 1	Cycle 2	Odd # cycles Begin at Cycle 3	Even # cycles Begin at Cycle 4	End of Treatment	Long-term Follow-up
	-28 days	Day 1 +/- 2 days	Day 1 +/- 2 days	Day 1 +/- 2 days	Day 1 +/- 2 days	35 days from last dose of study treatment +/- 5 days	Every 3 months (+/- 7 days) for 2 years from EOT
Informed consent	X						
Medical history	X						
Diagnosis and staging	X						
Physical Exam	X	X 	X	X	X	X	
Vital signs, wt, waist circumference  , ECOG performance status	X	X 	X	X	X	X	
AEs & concomitant medications, drug diary review 	X	X	X	X	X	X	
LABORATORY ASSESSMENTS							
CBC with differential (minimum to include: Hgb, WBC, Plt, ANC)	X	X 	X	X	X	X	
CMP 	X	X 	X	X	X	X	
Blood for metabolic indices 		X	X		X	X	
Homocysteine/cysteine 		X		X		X	

Cycle = 21 days	Screening	Cycle 1	Cycle 2	Odd # cycles Begin at Cycle 3	Even # cycles Begin at Cycle 4	End of Treatment	Long-term Follow-up
	-28 days	Day 1 +/- 2 days	Day 1 +/- 2 days	Day 1 +/- 2 days	Day 1 +/- 2 days	35 days from last dose of study treatment +/- 5 days	Every 3 months (+/- 7 days) for 2 years from EOT
Pregnancy test (serum) 	- 7 days	X 					
Diet/Exercise Diary		X	X	X	X		
24 Hour Dietary Recall Form		X					
DISEASE ASSESSMENTS							
CT chest, CT or MRI of abdomen and pelvis 	X				X 		X
MRI brain	X 						
Bone scan	X 				X 		
TREATMENT EXPOSURE							
ONC201		Days 3 and 4, weekly	Days 3 and 4, weekly	Days 3 and 4, weekly	Days 3 and 4, weekly		
MR diet		Days 1 - 5 weekly	Days 1 - 5 weekly	Days 1 - 5 weekly	Days 1 - 5 weekly		
CORRELATIVE STUDIES (SPECIMEN COLLECTION)							
Archival Tissue 	X						
Circulating tumor cells		X 	X 			X 	
Plasma methionine & methionine metabolites		X 	X 		X 	X 	
FOLLOW-UP							
Survival							X

- (1) Blood will be taken to assess metabolic indices at baseline, cycle 2 day 5, then day 5 of every other cycle, and at end of treatment. Indices are fasting: glucose, insulin, IGF-1, and leptin levels. If necessary, these labs may be drawn as early as day 2, but prefer to be as close to day 5 as possible without going over.

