## 8. BIOSPECIMEN STUDIES AND PROCEDURES

### 8.1 Tumor tissue

Subjects will be consented for use of archived tissue for analysis. To determine the effects of dietary MR on tumor expression of TRAIL receptors, mRNA levels of TRAIL-R1 and TRAIL-R2 will be determined by real-time PCR. In addition, quantitative immunofluorescence of cell surface TRAIL-R1 and TRAIL-R2 expression in breast tumor cells identified by cytokeratin expression will be determined by automated quantitative analysis (AQUA) of digitally captured images. These studies will be performed in the UW Carbone Cancer Center Translational Research Initiatives in

Pathology (TRIP) Lab under the supervision of our co-investigator [name]. We will also determine the effects of treatment on the expression of the cancer stem cell markers CD44 and CD24 by immunohistochemistry.

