### 13.2 Sample size and accrual

The primary objective is to evaluate efficacy of ONC-201 with dietary MR in metastatic TNBC. The study is designed as a single-arm phase II trial. The primary endpoint is ORR. Secondary endpoints include CBR at 4 months, PFS, OS, safety, metabolic indices and CTC TRAIL-receptor expression. The null hypothesis is that the probability of overall response is no more than 0.1, *i.e.*,  $H_0: p \leq 0.1$ , and the alternative hypothesis is  $H_1: p \geq 0.25$ .

In this single arm study, a Simon's two stage design will be utilized. The null hypothesis that the true ORR is 0.1 will be tested against a one-sided alternative. The study will be powered to detect an ORR of 25% with the combination of ONC201 with a methionine-restricted diet, using a power of 80% and a type I error rate of 10%. The first stage sample size will be 13. After testing the combination on 13 subjects in the first stage, the trial will be terminated if 1 or fewer subjects respond. If the trial goes on to the second stage, a total of 34 subjects will be studied (*i.e.* additional 21 subjects will be recruited). If the total number responding or having ORR is less than or equal to 5, the combination of ONC201 with a methionine-restricted diet will be rejected.

The estimated total sample size for the study is 34 subjects.

One subject was enrolled to the ONC201 +MR diet prior to changing the dosing schedule. This subject will be replaced for efficacy analysis, but will be considered part of the safety analysis.

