### 13.7.2 Analysis plans for secondary objectives

PFS and OS will be summarized using Kaplan-Meier estimates of the median survival times. Point estimates as well as 95 % confidence intervals will be provided. PFS based on degree of AR expression by IHC (AR >0% vs. AR  $\geq$ 10%) will be compared using the log-rank test. Additional exploratory analyses using proportional hazards model to control for other factors may be performed.

CBR at 4 months will be estimated according to RECIST 1.1, by dividing the total number of responders (complete plus partial responses plus CR or PR or stable disease (SD)), by number of subjects with measurable disease and the exact 95% confidence interval will be provided. In evaluating CBR, subjects with missing data will be considered non-responders. Also, duration of response (DOR) will be measured using Kaplan-Meier methodology. A 95% confidence interval will be provided for the median duration of response. Subjects who do not relapse will be censored at the day of the last objective tumor assessment. In evaluating response duration, non-responders will be excluded from analysis.

In addition, correlation analyses will be performed to assess the expression of TRAIL receptor in CTCs prior, during and upon progression of disease. Formal statistical tests will be performed based on the outcome types and the biomarker quantification.

Safety and Tolerability by NCI CTCAE v5.0 will be assessed by frequency tables. Also, metabolic indices in patients with metastatic TNBC treated with ONC-201 and a methionine-restricted diet will be assessed by frequency tables and descriptive statistics.

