#### **15.2 Case Report Forms and Submission**

Generally, clinical data will be electronically captured in OnCore and correlative results will be captured in OnCore or other secure database(s). If procedures on the study calendar are performed for standard of care, at minimum, that data will be captured in the source document. Select standard of care data will also be captured in OnCore, according to study-specific objectives. Please see the Data and Safety Oversight Process (DSOP) guidelines for further details.

The completed dataset is housed at UWCCC and is the sole property of the University of Wisconsin. It should not be made available in any form to third parties, except for authorized representatives of appropriate Health/Regulatory Authorities, without written permission from the sponsor-investigator.

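### Section 13.7.2 plans a log-rank test of PFS between two AR groups that overlap (AR >0% and AR ≥10%) and omits AR 0%; the groups need to be made mutually exclusive

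*Combined protocol and SAP*

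**What the plan says.** Section 13.7.2, under the plans for secondary objectives, specifies a comparison of "PFS based on degree of AR expression by IHC (AR >0% vs. AR" followed by a ≥ sign and "10%) will be compared using the log-rank test". The wording is a commitment; the next sentence of that section treats further proportional hazards modelling as optional and exploratory.

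No other part of the documents explains the AR groups:

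- The synopsis covers PFS without AR: "Time to event outcomes such as PFS and OS will be analyzed using Kaplan-Meier method and Cox proportional hazards regression".
- Section 13.2 lists the endpoints without AR: "Secondary endpoints include CBR at 4 months, PFS, OS, safety, metabolic indices and CTC TRAIL-receptor expression".
- Eligibility (3.1.1) uses ER, PR and HER2 only.
- The tissue work in 8.1 covers TRAIL-R1, TRAIL-R2 and "cancer stem cell markers CD44 and CD24 by immunohistochemistry"; AR is not among the assays.
- AR is missing from the abbreviations. It is taken here to mean androgen receptor, which is an assumption.

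Two places could supply AR from routine pathology. The study calendar has a screening item "Diagnosis and staging", and section 15.2 says "Select standard of care data will also be captured in OnCore, according to study-specific objectives".

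**The concern.** The two named groups are nested, and part of the population belongs to neither. Whoever runs the analysis must first decide what was meant, and the text gives no guide. The choice changes which subjects are compared and can change whether the result is called significant. If it were made after PFS by AR had been seen, the nominal error rate would no longer hold, and a later reader could not tell when it was made.

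The stake is limited. This is one secondary comparison, and no decision in the plan depends on it.

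**Working it through.** **1. The plan's own figures.** None is given for the AR comparison: no AR distribution, hazard ratio, alpha, sidedness or power. The only design figures are for ORR (13 then 34 subjects; stop at ≤1 response, reject at ≤5; rates 0.10 and 0.25). An exact two-stage binomial calculation gives type I error 0.0957 and power 0.811, in line with the stated 10% and 80%. AR plays no part in it.

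**2. Set logic.** Let a, b and c be the numbers with AR 0%, AR >0 to <10%, and AR ≥10%. The group AR >0% has b + c subjects and the group AR ≥10% has c. The overlap is c, the whole second group, and a subjects are left out. This needs no assumption. As an illustration with a/b/c = 17/7/10, the groups have 17 and 10 subjects, the same 10 are in both, and 17 of 34 are in neither.

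**3. Running it literally.** On that 17/7/10 mix, AR ≥10% subjects were entered in both groups and compared with a disjoint <10% vs ≥10% split (1,500 simulated trials, exponential PFS, no censoring, hazard ratio for AR ≥10% vs the rest):

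| Hazard ratio | As written: rejects | <10% vs ≥10%: rejects |
|---|---|---|
| 1 | 0.0% | 6.6% |
| 2 | 0.7% | 46% |
| 3 | 5.3% | 81% |

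The literal test does not hold its nominal 5% and has almost no power.

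**4. How much the choice of split matters.** Assumptions: 34 subjects, all with events, exponential PFS, two-sided 5% (|Z| > 1.96), 20,000 simulated trials per setting, four AR mixes. Split A is <10% vs ≥10%; split B is 0% vs >0%. Moving from A to B transfers the b middle subjects (3, 7, 6 or 13 of 34).

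| Mix a/b/c | No effect: A | No effect: B | Better of A and B | A and B disagree, no effect | A and B disagree, HR 0.5 at the 10% cut |
|---|---|---|---|---|---|
| 24/3/7 | 6.6% | 6.2% | 10.1% | 7.3% | 16.9% |
| 17/7/10 | 6.2% | 5.9% | 10.5% | 9.0% | 27.7% |
| 14/6/14 | 6.0% | 5.9% | 10.0% | 8.0% | 28.2% |
| 8/13/13 | 6.1% | 6.4% | 11.6% | 10.8% | 39.5% |

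With the HR of 0.5 placed at the 0% cut instead, the same simulation gives disagreement in about 26–40% of trials, so 17–40% covers both cases. Single tests sit slightly above 5% because the normal approximation is used with few events.

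**5. Precision once a split is fixed.** The 95% confidence limits are the hazard ratio divided and multiplied by exp(1.96 × √(1/e₁ + 1/e₂)), where e₁ and e₂ are the events per group. For 17/7/10 and split A: exp(1.96 × √(1/24 + 1/10)) = exp(0.738) = 2.09. Across the four mixes the factor is 1.96–2.30 for splits A and B. Across splits A, B and >0 to <10% vs ≥10%, power at HR 0.5 is 16–47% if the change lies at the 10% cut and about 6–50% if it lies at the 0% cut.

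**6. Early stopping.** The trial stops at 13 subjects if ≤1 respond. At ORR 10% the probability is 0.9¹³ + 13 × 0.1 × 0.9¹² = 0.254 + 0.367 = 0.62; at ORR 25% it is 0.75¹³ + 13 × 0.25 × 0.75¹² = 0.024 + 0.103 = 0.13. The comparison would then have only about 13 subjects.

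**The case against.** The best defence is that this is a drafting slip in a side analysis. No decision rests on it, any statistician would form disjoint groups before running it, and every size above comes from assumed AR mixes and effects. That stands as far as severity goes. It does not remove the defect, because several disjoint schemes fit the words and the documents do not choose between them.

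Three further points also stand.

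- It would be wrong to insist on a single pair of groups. Two separate cut-point tests, or three ordered groups, suit an analysis by degree of expression equally well.
- A reader might infer that AR data will not exist because 8.1 lists no AR assay. The documents do not support that. Existing pathology reports may supply AR, and the Study Procedures Manual, which section 15.1 says holds the data-entry guidance, is not among the documents.
- A reader might infer that the plan inflates the false-positive rate. It does so only if the split is picked after PFS by AR has been seen, and nothing in the documents suggests this. A choice made without that knowledge causes no inflation.

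A misread >0% in the PDF text cannot be excluded, but there is no sign of one; the <10% thresholds in 3.1.1 came through intact.

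**Conclusion.** The sentence is wrong as written, and the point is minor. The overlap and the omission of AR 0% follow from the definitions alone. The sizes do not: they hold for the four assumed mixes, 34 subjects with all events, and a two-sided 5% test.

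On those assumptions the two obvious splits disagree on significance in about 17–40% of trials at a hazard ratio of 0.5, and in 7–11% with no effect. Picking the better one after seeing the data gives about 10–12% false positives, against 6–7% for either fixed in advance. The comparison is not powered under any split examined, and stopping after stage 1 would leave it weaker still.

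A reader should not infer that the trial's main conclusion is at risk. The ORR decision, the two-stage rule and the overall PFS and OS estimates do not use AR.

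**What to change.** Before PFS by AR is examined, the sponsor should rewrite the one sentence in 13.7.2 so that the groups within each comparison are mutually exclusive. Any of these would do:

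- AR <10% vs AR ≥10%;
- AR 0% vs AR >0%;
- both of these, listed as two cut-point tests and both reported (with no effect, the chance that at least one is significant is the 10–12% above);
- three ordered groups (0%, >0 to <10%, ≥10%) with a k-sample or trend log-rank test.

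The sentence should add that subjects without an AR result are counted and left out, and that the comparison is not powered. If AR will not be available, delete the sentence.

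As a query only: define AR and state where the results come from, for example existing pathology reports.

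Cost: one sentence, and at most one baseline data field if AR is not already captured. No added subjects, samples or visits.

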### **6.3 Protocol therapy discontinuation**

In addition to discontinuation from therapy related to toxicities as outlined in section 6.1, a subject will also be discontinued from protocol therapy and followed up per protocol under the following circumstances:

- Documented disease progression
- Discontinue methionine restricted diet for weight loss grade 2 or higher
- The treating physician thinks a change of therapy would be in the best interest of the subject
- The subject requests to discontinue protocol therapy, whether due to unacceptable toxicity or for other reasons
  - If a subject decides to prematurely discontinue protocol therapy ("refuses treatment"), the subject should be asked if he or she may still be

contacted for further scheduled study assessments. The outcome of that discussion should be documented in the medical records.

- A female subject becomes pregnant
- If protocol therapy is interrupted for >21 days.

Subjects will be removed from protocol therapy, and the site investigator notified, when any of the criteria listed above apply. The reason for discontinuation of protocol therapy will be documented on the eCRF in OnCore.

Subjects who discontinue protocol therapy will be followed every 3 months for 2 years after the end of treatment visit. Survival status and anti-cancer therapy (to include only first cancer directed therapy after study) will be collected from review of medical records or via telephone follow up.

If subjects discontinue study treatment prior to disease progression, scans during follow-up will be completed per standard of care, but RECIST measurements must be completed until disease progression or start of new anti-cancer therapy.

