## 9.7 Evaluation of Best Overall Response

Target Lesions	Non-Target Lesions	New Lesions	Overall Response
CR	CR	No	CR
CR	Non-CR/ Non-PD	No	PR
CR	Not evaluated	No	PR
PR	Non-PD/ or not all evaluated	No	PR
SD	Non-PD or not all evaluated	No	SD
Not all evaluated	Non-PD	No	Non-evaluable
PD	Any	Yes or No	PD
Any	PD*	Yes or No	PD
Any	Any	Yes	PD

\*In exceptional circumstances, unequivocal progression in non-target lesions may be accepted as disease progression.

Subjects with a global deterioration of health status requiring discontinuation of treatment without objective evidence of disease progression at that time should be classified as having “symptomatic deterioration”. Every effort should be made to document the objective progression even after discontinuation of treatment.

In some circumstances it may be difficult to distinguish residual disease from normal tissue. When the evaluation of complete response depends on this determination, it is recommended that the residual lesion be investigated (fine needle aspirate/biopsy) to confirm the complete response status.

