### 9.8.3 Duration of Response

Duration of overall response—the period measured from the time that measurement criteria are met for complete or partial response (whichever status is recorded first) until the date that recurrent or progressive disease is objectively documented (taking as reference for progressive disease the smallest measurements recorded since treatment started).

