### 9.8.6 Progression-Free Survival

A measurement from the date of treatment initiation until the criteria for disease progression is met as defined by RECIST 1.1 or death occurs. Subjects who have not progressed will be right-censored at the date of the last disease evaluation.

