### 9.8.7 Overall Survival

Overall survival is defined by the date of treatment initiation to date of death from any cause.

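### Duration of response censors a responder who dies without documented progression, although PFS counts the same death as an event; a minor point, fixed by rewording the DOR rule

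*Combined protocol and SAP*

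**What the plan says.** Section 9.8.3 runs DOR from the time response criteria are first met "until the date that recurrent or progressive disease is objectively documented". Section 13.7.2 plans a Kaplan-Meier analysis in responders only, with a 95% confidence interval for the median, and gives the censoring rule: "Subjects who do not relapse will be censored at the day of the last objective tumor assessment". Neither place mentions death. Section 9.8.4 defines duration of complete response in the same way, but no analysis of it is planned.

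PFS in 9.8.6 runs "until the criteria for disease progression is met as defined by RECIST 1.1 or death occurs". OS in 9.8.7 uses death from any cause, so dates of death are collected.

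Two other passages bear on how such a death could arise. Section 9.7 foresees patients with "global deterioration of health status requiring discontinuation of treatment without objective evidence of disease progression at that time" and adds: "Every effort should be made to document the objective progression even after discontinuation of treatment". Section 6.3 says that, if treatment stops before progression, scans follow standard of care and "RECIST measurements must be completed until disease progression or start of new anti-cancer therapy". Survival and the first later cancer therapy are followed for 2 years. On treatment, scans are about 9 weeks apart (section 7, footnote 10).

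**The concern.** A responder who dies before progression is documented has not relapsed in the sense of 9.8.3, so the 13.7.2 rule takes her out of the risk set at her last scan. Readers commonly take a median DOR to say how long responders stay alive and free of progression. The written rule answers a different question: how long until progression, with death treated as if follow-up had merely ended. For the same patient, DOR is then censored while PFS has an event. No other section makes death a DOR event, and no sensitivity or competing-risk analysis of DOR is planned.

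At stake is one descriptive median and its interval. With only a handful of responders, a single such death can move that median.

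**Working it through.** **1. The plan's own figures.** From 13.2: 13 patients in stage 1, stop at 1 or fewer responses; 34 in total, reject the combination at 5 or fewer; ORR 10% against 25%. Exact binomial calculation gives type I error 0.096 (stated 10%) and power 0.811 (stated 80%). The design reproduces, and nothing below alters it.

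**2. How many responders DOR will rest on.** The chance of stopping at stage 1 is PET = P(Bin(13, p) ≤ 1) = 0.621 at p = 0.10 and 0.127 at p = 0.25.

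- Overall, E(R) = 13p + (1 − PET) × 21p. At 10%: 1.3 + 0.379 × 2.1 = 2.1. At 25%: 3.25 + 0.873 × 5.25 = 7.8.
- Given stage 2, E(R) = [13p − P(exactly 1 of 13)] / (1 − PET) + 21p. At 10%: (1.3 − 0.367)/0.379 + 2.1 = 4.6. At 25%: (3.25 − 0.103)/0.873 + 5.25 = 8.9.

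**3. Chance that the issue arises at all.** Let s be the share of response-ending events that are deaths without documented progression. The documents give no value, so s is assumed. The chance of at least one such death is E[1 − (1 − s)^R], averaged over the distribution of R given stage 2:

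| s | ORR 10% | ORR 25% |
|---|---|---|
| 10% | 37% | 59% |
| 20% | 62% | 84% |
| 30% | 78% | 94% |

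Over all trials at ORR 10%, including those stopped early, the chances are 18%, 31% and 40%.

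**4. Large-sample size.** Under constant independent hazards and continuous observation, censoring deaths turns a progression-or-death median m into m/(1 − s), a factor of 1.11, 1.25 or 1.43 for s = 10%, 20% or 30%. Scanning every 9 weeks reduces this, because progression is dated at the next scan but death on its own day. A simulation of 400,000 responders (exponential times, assumed medians of 4 to 12 months, the written rule censoring deaths at the last scan) gives medians longer by:

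- s = 10%: 8-10%
- s = 20%: 18-22% (at a 6-month median, 8.26 against 6.88 months)
- s = 30%: 32-38%

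**5. Small samples.** In 20,000 simulated trials (assumed 6-month median, two conventions for reading the Kaplan-Meier median), the share in which the two rules give the same median was:

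| Responders | s = 10% | s = 30% |
|---|---|---|
| 3 | 81-91% | 48-72% |
| 5 | 71-85% | 34-57% |
| 9 | 58-74% | 18-32% |

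The written rule shortened the median in 0-2% (s = 10%) and 0-4% (s = 30%) of trials.

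For scale, take 9 responders with exponential times and a 6-month median (mean 6/ln 2 = 8.66). The order-statistic interval from the 2nd to the 8th event has 96% coverage. Its expected ends are 8.66 × (1/9 + 1/8) = 2.0 months and 8.66 × (1/9 + 1/8 + … + 1/2) = 15.8 months.

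**6. Both directions (invented data).**

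- *Longer.* Six responders have events at 2, 4, 5, 7, 9 and 12 months. With all counted, S(5) = 0.5 and the median is 5. If the 4-month event is a death last scanned at 3, S is 5/6 at 2, 0.625 at 5 and 0.417 at 7, so the median is 7.
- *Shorter.* Progression at 4, 5 and 8; deaths at 6 and 7, both last scanned at 2. As written, three remain at risk after month 2, so S(4) = 2/3, S(5) = 1/3 and the median is 5. With deaths as events, S(4) = 0.8, S(5) = 0.6, S(6) = 0.4 and the median is 6.

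**7. Why a new-therapy rule goes with the fix.** Progression at 4, 6 and 8 months; two responders last scanned at 2 and 3 start new therapy and die at 15 and 16. If they are censored at the last scan before new therapy, the median is 6. If their late deaths count as DOR events, it is 8.

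**The case against.** The strongest reply is that the DOR text is consistent. Sections 9.8.3 and 13.7.2 agree with each other, 9.8.4 has the same form, and nothing promises that DOR and PFS share an event. This stands: the plan does not contradict itself. It uses a time-to-progression measure under a name that many will read otherwise.

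A reader might take the percentages in step 4 as the bias from informative censoring, since 9.7 and 6.3 describe patients who deteriorate and are then scanned less regularly. They are not that. The simulation makes progression and death independent, so the percentages are the distance between time to progression and time to progression or death. The documents give no basis for estimating dependence, and 9.7 asks for every effort to document progression, which should make such deaths fewer.

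The practical effect is also limited. At s = 10% most small trials show no change, and the confidence interval already planned is far wider than the shift. The shortening example needs deaths 4 to 5 months after the last scan, about twice the on-treatment interval.

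Two further inferences fail. The PFS sentence "Subjects who have not progressed will be right-censored at the date of the last disease evaluation", read alone, might seem to censor deaths too, but the sentence before it makes death an event. And the lack of a new-therapy rule for PFS does not justify rewriting 9.8.6 here: that is a separate trade-off on a listed secondary endpoint. For DOR, the current text in effect already censors such a patient near her last scan before the switch, because required RECIST measurement ends there. The rule has to be stated mainly because the fix makes death an event.

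What remains is that death in a responder is handled by implication, in a way that differs from PFS and usually flatters the median.

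**Conclusion.** The point holds and is minor. As written, DOR estimates time to progression among responders with death censored. When a responder dies without documented progression, the reported median is usually equal to or longer than the time to progression or death, and occasionally shorter. The large-sample gap is roughly a tenth, a fifth or a third of the median for s = 10%, 20% or 30%. It rests on assumed shares, assumed medians, exponential times and independent hazards, none of which the documents supply. There may be no such death in the trial. DOR is listed neither among the objectives (2.2) nor among the secondary endpoints in 13.2, and it carries no hypothesis or decision rule. ORR, the Simon design and OS do not change.

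**What to change.** In 9.8.3 and 13.7.2, end DOR at the first of documented recurrence or progression or death from any cause, and censor responders who are alive without progression at the last tumor assessment. For DOR only, add that a responder who starts new anti-cancer therapy before progression is censored at the last assessment before that therapy, so that a death long after scanning stopped does not count as the end of response. Leave 9.8.6 as it is. Settle the wording before response data are analysed, because with a handful of responders a later choice would be open to the charge of being data-driven.

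The cost is one or two sentences in each of the two sections and no new data: dates of death are collected for OS, and the first therapy after study is already recorded (6.3). The reported DOR will usually be the same or slightly shorter, and censoring at new therapy may itself be informative.
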